## 2 STUDY OBJECTIVES AND ENDPOINTS

### 2.1 Primary objective

Study design

This is a multi-center non-inferiority two arm randomized controlled trial. Results of MIS are expected to be non-inferior in terms of reoperations, serious complications, surgical site infection, pain and fusion rates compared to open surgery.

Definition of MIS:

Minimal invasive surgery (MIS) is here defined as a muscle salvage technique. Minimal invasive surgery is defined such that the posterior elements of the spine are not exposed and the spinal musculature is not detached from the posterior elements of the spine. That means that the erector spinae musculature is not detached from the spinous processes and the laminae, except for the exposure needed for the actual screw insertion. The surgeon is free to use either a long incision or multiple short incisions.

The arms consist of:

1. *Intervention group*

Patients operated with MIS: Minimal invasive surgery. The surgeon will be free to choose the method of screw placement. 3D-navigation, RAS, free hand technique or combinations of these may be used for screw placement. A long skin incision and subcutaneous multiple incisions are performed. The erector spinae musculature is not detached from the spinous processes and the laminae, except for the exposure needed for the actual screw insertion. Each screw is inserted through an incision in the musculature. The surgeon may choose to do decortication of all or some of the facet joints in the surgical area.

2. *Control group*

Patients operated with open surgery: Traditional open surgery. The surgeon will be free to choose the method of screw placement. 3D-navigation, RAS, free hand technique or combinations of these may be used for screw placement. A long skin and subcutaneous incision is performed. The posterior elements of the spine are exposed and the spinal musculature is detached from the posterior elements of the spine. The whole surgical area is exposed and all screws are inserted through this area. Separate incisions for screw placement in the musculature are not needed. The surgeon may choose to do decortication of all or some of the facet joints in the surgical area.

Clinical Study Protocol	Unique protocol ID	MISCOS
	Version No:	1.1
	Date:	2025-09-27

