## 3 STUDY DESIGN AND PROCEDURES

### 3.1 Overall study design and flow chart

This is a multi-center parallel assignment two arm randomized controlled trial (Figure 1). The trial will use a pragmatic approach and use existing equipment and document handling at the participating centers. Data from the existing quality registries for spine surgery will be extracted for outcome assessments.

Randomization between the two treatment arms will take place approximately a week preoperatively, as close to the operation day to minimize selection bias. Postoperative, blinding of the patients and health care personnel will be done.

[figure not shown]
The surgeons will be the only personnel related to patient follow-up that will not be blinded. However, the majority of the analyses, all postoperative imaging and record data collection and analysis will be performed by blinded reviewers.

Patient reported outcomes will be assessed without influence of the care giver.

Clinical Study Protocol	Unique protocol ID	MISCOS
	Version No:	1.1
	Date:	2025-09-27

The Uppsala University hospital performs approximately 80 spine deformity surgeries yearly and it is estimated that  $1/4$  of these meet the inclusion criteria for the study. Similar estimations are done for the rest of the centers with a total enrolment of approximately 50 patients per year. Our time plan includes study start (mid 2025), last patient included (2028) and last 2 year follow up (2029). Registry outcome data are collected preoperatively, at 1 year and 2 years. Registry data may also be collected at 5 and 10 years. The study may have come to an end 2038. However, delays in studies such as these are not uncommon.

Figure 1: Flowchart

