### 5.5.1 Technical problems encountered during surgery

If a technical problem with the 3D/navigation system or RAS system is encountered during surgery, the patient will be kept in the group to which he or she was randomized. This means that a possible MIS approach needs to be converted to open technique to enable screw placement by free hand technique. The patient will remain in the group to which he or she was randomized to and will not be replaced.

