## 7 STATISTICS

### 7.1 Sample size calculation

In order to use the win-odds method for a non-inferiority study we performed more than 1000 simulations using the statistical software R. We used the primary variables listed in 6.1 to calculate our sample size and assumed that the outcomes are independent and that the outcomes were equally distributed among study arms (i.e. we simulated a win-odds of 1.0). We set the power of the study to 80% with a lower limit of confidence interval for win-odds (also called non-inferiority limit) to above 0.60 and calculated a sample size of 150 individuals divided into two treatment arms. We set the possible number of dropouts until the 2-year follow-up to 20%, and the total sample size therefore adjusted to 180 individuals.

**7.1.1** What is a non-inferiority limit. The non-inferiority limit is the probability of a patient in the active arm (minimally invasive procedure) to win over a control patient given an evenly distributed number of ties [6].

**7.1.2** In the case that the MIS group shows slight benefits compared to the open surgery group then the non-inferiority limit will shift towards 1.0 as the win odds will be greater than 1.0 which was assumed in the sample size simulation.

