### 7.2 Statistical analysis

#### 7.2.1 Primary variables

We selected the above described seven variables in hierachic order to conduct a win-odds analysis. The variables were selected based on the clinical impact that they have on the patient. The method of win-odds was first introduced as win-ratio [7] in order to analyze composite endpoints based on clinical priorities. The method compares each treatment subject to all controls and the outcome is registered as "win", "lose" or "tie". In order to handle large numbers of ties the win-odds was introduced [8] that assigns 50% of the ties to both the numerator and the denominator. Particularly in non-inferiority trials the use of win-odds instead of win-ratio may be more suitable since ties in non-inferiority studies may represent a comparable treatment effect and their number is substantial [6].

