#### 7.2.2 Secondary variables

For the secondary variables descriptive statistics will be used to characterize the data; means and 95% confidence intervals will be used for parametric data, medians and interquartile ranges for non-parametric data, and number (proportions) for categorical data. For groups comparisons t-test or ANOVA will be used for parametric distributed data and Wilcoxon, Mann-Whitney or Kruskal-Wallis test will be used for non-parametric distributions respectively, along with post hoc analysis. Categorical data will be compared with Chi-square, McNemar or Sign tests.

Clinical Study Protocol	Unique protocol ID	MISCOS
	Version No:	1.1
	Date:	2025-09-27

Data from the different groups will be compared based on the 'intention to treat' principle. An intention to treat (ITT) analysis means that all patients, regardless of treatment change, loss to follow-up or drop-out, remain in the analysis of the group to which they were randomized. Statistical expertise blinded for treatment allocation will perform the statistical analyses.

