### 8.2 Data storage and management

All data should be recorded, handled and stored in a way that allows its accurate reporting, interpretation and verification. All source data including informed consents, the completed study database, original protocol with amendments and the final report will be stored at the Uppsala University Hospital and Uppsala University for a minimum period of 10 years after termination of the trial.

Clinical Study Protocol	Unique protocol ID	MISCOS
	Version No:	1.1
	Date:	2025-09-27

At the conclusion of the study, the occurrence of any protocol deviations will be determined. After these actions have been completed and the database has been declared to be complete and accurate, it will be locked and available for data analysis.

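### ITT is the only analysis stated for a non-inferiority trial that foresees MIS-to-open conversion; a supportive per-protocol win-odds analysis would be a cheap improvement

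*Protocol*

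**What the plan says.** Protocol 2.1 sets the design: "This is a multi-center non-inferiority two arm randomized controlled trial". Section 7.1 sets the criterion, a "lower limit of confidence interval for win-odds (also called non-inferiority limit) to above 0.60". Section 7.2.1 describes the primary method ("We selected the above described seven variables in hierachic order to conduct a win-odds analysis") and does not name an analysis set. The closing paragraph of 7.2.2 gives the only analysis principle in the protocol, ITT, under which "all patients, regardless of treatment change, loss to follow-up or drop-out, remain in the analysis of the group to which they were randomized".

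Section 5.5.1 covers failure of the navigation or robotic system during surgery: "This means that a possible MIS approach needs to be converted to open technique". It adds: "The patient will remain in the group to which he or she was randomized to and will not be replaced". No conversion from open surgery to MIS is described. Section 8.2 says: "At the conclusion of the study, the occurrence of any protocol deviations will be determined". It does not link those deviations to any analysis. Section 3.1 describes the trial's character: "The trial will use a pragmatic approach".

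**The concern.** In a superiority trial, mixing the treatments usually works against the claim. In a non-inferiority trial it can work for it. The crossover described here runs one way: some patients allocated to MIS receive the control procedure and are counted as MIS. If they then fare like open patients, the two arms become more alike and the win odds move towards 1, away from the 0.60 limit. A finding of non-inferiority could then rest partly on patients who had open surgery. With ITT as the only stated analysis, a reader could not tell how much.

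**Working it through.** **Inputs from the protocol.** Limit 0.60, true win odds 1.0, power 80%, 150 patients before and 180 after allowance for dropout (7.1); 1:1 allocation (5.5), hence 90 per arm.

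**Assumptions, because the protocol gives no figure.** Conversion c of 5%, 10% or 20% of the MIS arm; a two-sided 95% interval, with 90% as an alternative; converted patients fare like open patients unless stated otherwise.

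**The plan's own figure.** On the log win-odds scale with the Mann-Whitney variance, N = (16/3) × f × (z_alpha + z_beta)² / ln(0.60)², where f ≤ 1 allows for ties. With a 95% interval, f = 1 gives 160 and f = 0.93 gives 149. With a 90% interval, f = 1 gives 126. So 150 is plausible with a 95% interval and a modest share of ties. It cannot be reproduced strictly, because neither the confidence level nor the outcome distributions are stated.

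**Step 1: dilution.** Let P be the probability that an MIS patient wins, counting half the ties; win odds = P/(1 − P). At the limit, P = 0.60/1.60 = 0.375. Under ITT, P_ITT = 0.5c + (1 − c) × P_delivered.

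| Conversion | ITT win odds when MIS as delivered is 0.60 | Win odds of MIS as delivered when ITT is 0.60 |
|---|---|---|
| 5% | 0.38125/0.61875 = 0.616 | P = 0.350/0.95 = 0.368; 0.583 |
| 10% | 0.3875/0.6125 = 0.633 | P = 0.325/0.90 = 0.361; 0.565 |
| 20% | 0.400/0.600 = 0.667 | P = 0.275/0.80 = 0.344; 0.524 |

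**Step 2: how often non-inferiority is declared when MIS as delivered has win odds 0.60.** Simulation with 20,000 trials per setting, a normal outcome without ties, 90 per arm, and a claim if the lower limit exceeds 0.60:

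| Conversion | ITT, 95% interval | ITT, 90% interval | Per-protocol, 95% interval, conversion unrelated to prognosis |
|---|---|---|---|
| 0% | 2.5% | 5.0% | 2.5% |
| 5% | 3.4% | 6.9% | 2.4% |
| 10% | 4.7% | 8.5% | 2.4% |
| 20% | 8.6% | 14.6% | 2.5% |

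A closed-form check at N = 180 uses SE = √[(N + 1)/(12 × (N/2)²)] / [P(1 − P)]. For c = 10%: √(181/97,200) = 0.0432; divided by 0.3875 × 0.6125 = 0.2373, SE = 0.182. Then ln(0.6327/0.60) = 0.0530; 0.0530/0.182 − 1.96 = −1.67, giving 4.8%. The same formula gives 3.5% at 5% and 8.5% at 20%. With 72 per arm (90 × 0.80, after 20% random loss), the simulated ITT rates are 3.4%, 4.4% and 7.8%.

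**Step 3: other assumptions about converted patients.** If they fare worse, with 1.5 times the MIS deficit, ITT declares non-inferiority in 2.3%, 1.9% and 1.2% of trials at 5%, 10% and 20% conversion (95% interval). The shift reverses.

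If conversion is related to worse prognosis (assumed correlation 0.3), per-protocol itself declares non-inferiority in about 3.6%, 5.4% and 8.8%, against about 3.0%, 4.4% and 7.6% for ITT in that setting. Removing only the poorer-prognosis MIS patients flatters the MIS arm.

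**Step 4: if the procedures are truly equal** (win odds 1.0, 90 per arm, 95% interval, conversion unrelated to prognosis):

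| Conversion | ITT meets the limit | Per-protocol meets the limit | ITT meets it, per-protocol misses it |
|---|---|---|---|
| 5% | 83.2% | 82.3% | 2.1% |
| 10% | 84.2% | 82.3% | 3.5% |
| 20% | 83.4% | 78.7% | 6.5% |

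**The case against.** The strongest reply is that nothing here is an error. ITT answers the treatment-policy question, suits a pragmatic trial and keeps its nominal error rate for that question. Supportive analysis sets are often left to a SAP, nothing in section 7 excludes one, and 8.2 already has deviations determined before database lock. All of this stands, and it limits the point to an improvement.

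The size is also open to challenge. The 5% to 20% range is assumed. The only conversion described follows a technical failure, and 2.1 and 5.1 also allow free-hand screw placement within MIS, so conversion may be rare. At 5% the change is from 2.5% to 3.4%.

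A reader might go further in three ways that the protocol does not support:

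- That ITT applies only to the secondary variables because of its heading. The paragraph is worded generally and closes section 7.2, and 5.5.1 keeps converted patients in their arm without limiting this to any endpoint. The natural reading is that ITT covers the primary win odds too.
- That per-protocol is the more reliable test because it holds near 2.5% in Step 2. This holds only if conversion is unrelated to prognosis, which the protocol cannot show.
- That the approach delivered goes unrecorded because the legible part of the Appendix 1 form has no such field. The form's graphics are not legible in the text at hand, and 5.7 collects detailed surgical data from hospital files.

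What remains is that the protocol itself combines a non-inferiority objective, a one-way conversion rule and a single stated analysis that is not conservative in that setting.

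**Conclusion.** The point holds as a cheap improvement. ITT should stay primary. If converted patients fare like open patients, it moves win odds of 0.60 for MIS as delivered to 0.616, 0.633 or 0.667 at 5%, 10% or 20% conversion, and the stated analysis would not reveal this. The corresponding rates of declaring non-inferiority must not be read as an inflated type I error of the planned analysis: they measure ITT against a different question, the effect of MIS as delivered. Their size depends on the assumed conversion rate and confidence level. Their direction depends on how converted patients fare, so it has to be shown in the data and not presumed. Confidence is medium.

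**What to change.** State in 7.2.1 that the primary win-odds analysis is by ITT, with all randomised patients in their allocated arm. Add a pre-specified supportive per-protocol win-odds analysis, restricted to patients in whom the allocated approach was delivered, against the same 0.60 limit. Report it beside ITT with the number converted, and require any disagreement to be explained before MIS is called non-inferior, without giving the supportive analysis a veto. Record the approach delivered for each patient from the surgical data already collected under 5.7.

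The cost is a few sentences, one recorded item and one extra analysis, with no added patients or visits. The drawbacks are a smaller set, possible selection bias, and some chance disagreement when the procedures are truly equal (Step 4), which is why disagreement calls for explanation and is not an automatic failure.

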## 8 DATA MANAGEMENT

### 8.1 Recording of data

Data will be collected from several sources (Table 2). Data primarily collected by Swespine will upon request from the research group be transferred into the study database.

**Table 2.** Collection of data.

Collected by	Swespine/Redcap /Spine Registry	Patient records in each center	Intra- and postoperative imaging
Type of data			
Additional spine surgery	X	X	X
Data on complications and adverse events	X	X	
PROMS	X		
Preoperative planning		X	
Screening question answers	X		
Assessment of radiologically healed fusion			X
Inpatient stay		X	
Total procedure time and blood loss	X		
Health economics		X	
Intraoperative neuromonitoring	X		
Data on planned and actual screw paths		X	X

### 8.2 Data storage and management

All data should be recorded, handled and stored in a way that allows its accurate reporting, interpretation and verification. All source data including informed consents, the completed study database, original protocol with amendments and the final report will be stored at the Uppsala University Hospital and Uppsala University for a minimum period of 10 years after termination of the trial.

Clinical Study Protocol	Unique protocol ID	MISCOS
	Version No:	1.1
	Date:	2025-09-27

At the conclusion of the study, the occurrence of any protocol deviations will be determined. After these actions have been completed and the database has been declared to be complete and accurate, it will be locked and available for data analysis.

## 9 QUALITY CONTROL AND QUALITY ASSURANCE

The research coordinator will have regular contacts with the research team and participating subjects to confirm that the investigational team is adhering to the protocol. The investigators should ensure that all persons assisting with the trial are adequately informed and trained about the protocol and their trial related duties.

### 9.1 Audits and inspections

Authorized representatives may perform audits. The investigators must ensure that all study documents are accessible for auditing and inspection. The purpose of an audit or inspection is to systematically and independently examine all study-related activities and documents, to determine whether these activities were conducted, and data were recorded, analyzed and accurately reported according to the protocol, and any applicable regulatory requirements.

## 10 ETHICS

The study will be performed in accordance with the protocol, with the latest version of the Declaration of Helsinki, and applicable regulatory requirements. The Swedish national Ethical Review Agency will review the study protocol.

The Principal Investigator is responsible for informing the Ethical Review Agency of any amendment to the protocol, in accordance with local requirements.

#### **Informed consent:**

The investigators will ensure that the subject is given written information about the nature, purpose and possible risks and benefits of the study. Subjects must also be notified that they are free to discontinue from the study at any time. The subject should be given the opportunity to ask questions and allowed time to consider the information provided.

The subject's signed and dated informed consent must be obtained before conducting any procedure specifically for the study.

The original, signed Informed Consent Form (ICF) must be stored at each study site.

#### **Subject data protection:**

The Informed Consent Form will incorporate wording that complies with relevant data protection and privacy legislation, and about the collection of data for the purposes of the study.

The Informed Consent Form will explain that study data will be collected from questionnaires, hospital files, images and health databases/registries and will be stored in a computer database, maintaining confidentiality in accordance with national data legislation.

Clinical Study Protocol	Unique protocol ID	MISCOS
	Version No:	1.1
	Date:	2025-09-27

### **Insurances:**

The study subjects are covered by the Swedish Patient Injury Act, and similar in international centers.

## **11 PROTOCOL DEVIATIONS AND AMENDMENTS**

Modifications to the signed protocol are only possible through approved protocol amendments. Details of non-substantial amendments are to be clearly noted in the amended protocol.

In case of a substantial protocol amendment (e.g. change of; main purpose of the trial, primary/secondary variable, measurement of primary variable), the Ethical Review Agency must be informed and should be asked for its opinion/approval prior to implementation of amended protocol, as to whether a full re-evaluation of the ethical aspects of the study is necessary by the committee. This should be fully documented.

The Investigator must not implement any deviation from, or change to the protocol, without discussion with, and agreement by the study group and prior review and documented approval/favorable opinion of the amendment from the Ethical Review Agency, except where it is necessary to eliminate an immediate hazard to study subjects, or where the change(s) involves only logistical or administrative aspects of the study (e.g. change of telephone numbers).

## **12 REPORT AND PUBLICATIONS**

After completion of the study, the results will be analyzed, and a clinical study report will be prepared. Upon study completion and finalization of the study report the results of this trial will be submitted for publication and posted in a publicly accessible database of clinical trial results.

## **13 STUDY TIMETABLE**

### **13.1 Study period**

Estimated subject enrollment start: mid 2025

Estimated subject enrollment stop: mid 2028

Estimated subject last 2-year follow-up: mid 2030

Estimated study end: mid 2038

Definition of "End of study"

[figure not shown]
End of study is defined as the last follow-up of the last subject.

Clinical Study Protocol	Unique protocol ID	MISCOS
	Version No:	1.1
	Date:	2025-09-27

## Appendix 1: Operation protocol MISCOS clinical trial

### Designations

-  Planned screw
-  Positioned screw according to plan
-  Repositioned screw
-  Removed screw
-  Not placed screw (not attempted)

Total planned screws.....	
Total inserted screws.....	
Repositioned screws.....	
Removed screws.....	
Not placed screws.....	
Procedure time.....	
Blood loss.....	
Neurophysiology.....	
Inpatient stay.....
